2.1 Primary Objective

Our *overall objectives* in this proposal are to (i) assess the impact of two social accountability approaches on contraceptive use, (ii) assess the impact of these approaches on community empowerment and quality of care, and (iii) assess the scalability of these approaches to additional settings. The proposed aims will be carried out in Kisumu County (Kenya) in close collaboration with the county health department.

Aim 1: Estimate the impact of two social accountability interventions on modern contraceptive use. We will collect pre- and post-intervention measures of current modern contraceptive use in a representative sample of 2,268 women of reproductive age residing in Kisumu, using two independent cross-sectional surveys. We will use a *difference-in-difference (DiD) model* to estimate differential change in contraceptive use over time in each of the two treatment areas versus the control area.

Aim 2: Estimate the impact of two social accountability interventions on community empowerment and **quality of care.** In addition to measuring contraceptive prevalence, our pre- and post-intervention surveys will

measure changes in community empowerment and the quality of family planning service delivery as important outcomes along the causal pathway from treatment to increased contraceptive use. Understanding the impact of the interventions on these intermediate outcomes will increase knowledge of the mechanisms by which the social accountability approach impacts health outcomes. As in Aim 1, we will use DiD models to estimate differential change for these intermediate outcomes over time.

Aim 3: Using implementation science methods, assess the quality, scalability, and replicability of two social accountability interventions for uptake by the public-sector healthcare system. Little is known about how citizens and providers experience monitoring of providers. Negative perceptions from citizens or providers could ultimately reduce engagement in these approaches and hinder positive and sustainable outcomes. We will use validated measures of provider job satisfaction in the facility survey, as well as in-depth interviews with providers and community members, to assess local perspectives on citizen monitoring. Additionally, we will conduct focus groups with key facilitators in the two interventions to better understand implementation challenges and potential barriers to scale-up.

3 INVESTIGATIONAL PLAN (brief overview)

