3.2 Allocation to Treatment Groups

This is a three-arm cluster randomized experiment in which all 147 public healthcare facilities located in Kisumu county will be randomly assigned to one of three study arms: 1. The Community Score Card treatment arm, 2. The Citizen Report Card treatment arm, and 3. The control arm. Each study arm will contain approximately 43 facilities, which, on average, serve approximately 2,500 households each. Prior to randomization, we will ensure the three arms each contain similar numbers of each type of facility by first stratifying by facility type, a designation that includes three categories: 1. clinics and dispensaries (the smallest public facility type); 2. health centers; and 3. hospitals (sub-county or county hospitals).

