6 STATISTICAL CONSIDERATION

1.1 Primary Endpoint

Aim 1 Methods: Estimate the Impact of Two Social Accountability Interventions on Modern Contraceptive Use.

Overview. Weak accountability mechanisms in public-sector facilities result in poor provider performance, creating barriers to family planning use among women with a desire to space or limit future pregnancy. The *objective* of this aim is to estimate the impact of the Community Score Card and the Citizen Report Card, relative to the control arm, on current use of a modern contraceptive method. To attain this objective, we will test the *working hypothesis* that social accountability efforts result in increased community empowerment, provider performance, and service utilization which, in turn, increases contraceptive use. Our *approach* to testing the working hypothesis will be to use a difference-in-difference (DiD) model to estimate differential change over time in each of the two treatment areas versus the control area. The *rationale* for this aim is that the results will contribute to a nascent body of literature on the impact of social accountability efforts to increased contraceptive use. Such findings are important because they inform much needed knowledge of effective strategies for reducing unmet need for women living in LICs.

Research Design. To assess the causal effect of the interventions, we will use a difference-indifference (DiD) model to estimate differential change over time in each of the two treatment areas versus the control area. The DiD model is commonly used in the social sciences [45, 46] and is described as follows:

Y=60 + 61POST + 62T1 + 63(POST*T1) + 64T2 + 65(POST*T2) + 64X + ui (1)

In this equation, Y is a binary variable for current modern contraceptive use (0=non-use; 1=use), attained by asking participants, "Are you (or your partner) currently doing something or using any method to delay or avoid getting pregnant?" We will define modern contraceptive methods to include female or male sterilization, intrauterine device, implant, injectable contraception, oral contraceptive pill, or male or female condom.

Stacking pre- and post-data, POST is an indicator variable (0=baseline;1=endline) and T1 and T2 are indicator variables for assignment to the Community Score Card or Citizen Report Card, respectively (1), or control (0). Intervention protocol template_Draft_29AUG2016

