The interaction between POST and T1 or T2 gives the difference between the change in the value of Y in either treatment group versus the same change in the control group. Equation (1) also includes a vector, X, of demographic characteristics. For any covariates that are not balanced across the study arms we will control for them in the regression, using their baseline values [47]. These covariates could include age, religion, ethnicity (tribal group), marital status, literacy/education, parity, distance to public facility, and household wealth. This model can also be used to test whether there is a large difference between the treatments by testing the equality of β 3 and β 5.

Expected Outcomes. This aim is expected to provide critical knowledge of whether social accountability efforts can increase family planning use in LICs. Additionally, this aim will determine whether the two primary approaches to community engagement are largely different in their impact on women's contraceptive behavior. This work is crucial to global efforts to address facility-level barriers to contraceptive use.

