6.1 Sample Size and Power

For the *individual*-level surveys, we estimate a design effect of 1.56 for modern contraceptive prevalence due to our cluster-based sampling procedure, based on information provided in the 2014 Kenya Demographic and Health Survey (KDHS) Final Report, Appendix B, Table B2. We calculate our necessary sample size assuming 1.) 50% current modern contraceptive prevalence in Kisumu; 2.) 42 clusters in each study arm [clusters=facility catchment areas (All public facilities have a catchment area which is clearly defined, mutually exclusive, and exhaustive); we are allowing for potential closure of one facility per arm)]; 3.) an effect size of two standard deviations (which correlates to a change in the prevalence of modern contraceptive use of approximately 10 percentage points). With these parameters, we will need to survey 18 women in each of the 42 clusters in each of the three study arms, resulting in a total sample size of 2,268 women of reproductive age in the individual-level surveys. The 18 women sampled from each cluster will be selected at random. We will follow KDHS procedures in cases where there is more than one eligible woman in the household.

For the *facility*-level surveys we will measure family planning service quality and negative provider behaviors via interviews with one to ten providers, depending on total staff at each of the 147 facilities. This will result in approximately 385 provider interviews, with approximately 128 in each study arm. Unannounced visitors and mystery clients will also be deployed to secure less biased estimates of provider absenteeism, informal fee solicitation, and disrespectful/biased treatment of clients; mystery clients will also collect data on traditional measures of family planning service quality such as choice of methods and information on side effects. All 147 facilities in Kisumu will receive two unannounced visits and three mystery client visits.

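### The primary model's covariates are chosen by an undefined imbalance rule rather than fixed in advance for prognostic value, which forgoes a modest gain in precision

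*Combined protocol and SAP*

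**What the plan says.** Section 6, under Primary Endpoint (Research Design), sets out the DiD regression for Aim 1 and adds: "Equation (1) also includes a vector, X, of demographic characteristics". The content of X is then governed by one rule: "For any covariates that are not balanced across the study arms we will control for them in the regression", with the covariates' baseline values to be used. The candidates follow as a list of possibilities: "These covariates could include age, religion, ethnicity (tribal group), marital status, literacy/education, parity, distance to public facility, and household wealth".

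The plan gives no test, threshold or standardised difference that would make a covariate unbalanced, and it does not say when balance is judged. The Statistical Methods part of Section 6 and Section 6.1 add nothing on covariates.

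Three other statements bear on the point:

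- Women are measured "using two independent cross-sectional surveys" (Section 2.1), so the endline women are not the baseline women.
- Facilities are allocated after "first stratifying by facility type, a designation that includes three categories" (Section 3.2). Facility type is not among the candidate covariates.
- Aim 2 uses the same kind of DiD model, so whatever is unclear here carries over to those outcomes.

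**The concern.** Facilities are randomised, so an imbalance between arms is a chance event. It does not show whether the covariate predicts contraceptive use, and that is what determines how much precision adjustment buys. A rule triggered by imbalance can leave out age or marital status because they happen to look balanced, and bring in a weak predictor because it does not.

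The repeated cross-sectional design adds a second difficulty. A DiD estimate is moved by sampling imbalance among the endline women as much as by imbalance among the baseline women. Balance in the baseline sample does not reveal the fresh sampling imbalance in the endline sample. Endline women also have no baseline values of their own to adjust for.

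At stake are the pre-specification of the primary model and some precision from characteristics the plan already proposes to use. Precision is scarce here: Section 6 says that sample size limits rule out subgroup testing.

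**Working it through.** **The plan's own figure.** Section 6.1: 18 women × 42 clusters × 3 arms = 2,268 per survey, which agrees with the stated total. Two surveys give 2 × 2,268 = 4,536 records. This point does not disturb that figure.

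**How often chance would trigger the rule.** The plan states no test. Assume one independent check per listed covariate at 5%, with randomisation working as intended.

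- Expected number flagged: 8 × 0.05 = 0.4.
- Chance of at least one flag: 1 − 0.95^8 = 0.337, about 34%.

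In roughly two trials out of three nothing would be flagged and the primary model would be unadjusted.

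**What a fixed set would gain.** Inputs from Section 6.1: prevalence 50%, design effect 1.56, 18 women per cluster. Assumptions: the design effect applies at 18 per cluster; the correlation R of catchment effects between waves is 0.3 to 0.7; covariates explain a share r² of 0.05 to 0.20 of within-catchment variance. The documents give neither R nor r².

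- Intraclass correlation = (1.56 − 1)/17 = 0.033.
- Total variance = 0.5 × 0.5 = 0.25. Between catchments: 0.25 × 0.0329 = 0.00824. Within: 0.2418, or 0.2418/18 = 0.01343 per catchment mean.
- The variance of a catchment's change is proportional to 0.00824(1 − R) + 0.01343(1 − r²).

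At R = 0.5 the unadjusted value is 0.00412 + 0.01343 = 0.01755. With r² = 0.10 it becomes 0.00412 + 0.01209 = 0.01621, which is 7.7% less variance, and the standard error (SE) is multiplied by √0.923 = 0.961. Reductions in the DiD SE:

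| r² | R = 0.3 | R = 0.5 | R = 0.7 |
|---|---|---|---|
| 0.05 | 1.8% | 1.9% | 2.1% |
| 0.10 | 3.6% | 3.9% | 4.3% |
| 0.20 | 7.3% | 8.0% | 8.8% |

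**Whether the imbalance rule captures that gain.** A simulation used 3 arms × 42 catchments × 18 women × 2 waves, eight equally prognostic covariates, intraclass correlation 0.033, between-wave correlation 0.5, a continuous outcome with standard deviation 0.5 standing in for the binary one, and 800 runs per setting. The rule adjusted for covariates whose baseline catchment means differed across the three arms at p < 0.05. Here r² is the covariates' share of total variance. Empirical SE of the DiD estimate:

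| r² | No adjustment | Imbalance rule | All eight |
|---|---|---|---|
| 0.05 | 0.0408 | 0.0410 | 0.0404 |
| 0.10 | 0.0411 | 0.0410 | 0.0392 |
| 0.20 | 0.0406 | 0.0405 | 0.0377 |

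At least one covariate was flagged in 31-34% of runs, in line with the 34% above. The rule is indistinguishable from no adjustment. Relative to the rule, the fixed set lowers the SE by 1 − 0.0392/0.0410 = 4.4% at r² = 0.10 and 1 − 0.0377/0.0405 = 6.9% at 0.20. At 0.05 the difference is within simulation error.

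**The case against.** The strongest reply is textual. The plan first says, without condition, that the model includes X, and it never says that covariates enter only if unbalanced. One could read it as always including X and adding anything unbalanced. That reading is possible but strained: the members of X are never fixed, and the imbalance sentence would be redundant if all eight were always in. Even on that reading the adjustment set is unspecified, so the same change is needed.

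A reader might infer that the analyst could pick the model after seeing the results. The documents do not support that. The rule refers to baseline values; if balance is judged on the baseline survey alone, the set is settled before any endline outcome exists. The plan is silent on the timing, which is a gap in documentation and not evidence of selective choice.

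A reader might also infer that baseline balance is uninformative about the endline. That goes too far. The same catchments are sampled in both waves, so catchment-level differences in wealth, ethnicity or distance can persist, and the persistent part largely cancels in the DiD. The criticism holds for the fresh sampling imbalance.

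One might count 16 pairwise checks (eight covariates, two treatment-control contrasts) and reach a 56% chance of a flag. The plan speaks of balance across the arms and states no pairwise tests, and such contrasts share a control arm, so they are not independent. Eight checks and 34% fit the wording better.

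Finally, the gain is modest and depends on an assumed r². That stands.

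**Conclusion.** The concern holds in limited form. The plan fixes neither the primary model's adjustment set nor a criterion for imbalance, and the rule it gives selects on chance imbalance instead of prognostic value. That conclusion rests on the text and needs no numerical assumption.

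The size rests on assumptions. The 34% needs eight independent 5% checks. The 2-8% reduction in SE is for a between-wave correlation of 0.5 and covariates explaining 5-20% of within-catchment variance; over correlations of 0.3 to 0.7 the range is 1.8-8.8%. It also takes the design effect of 1.56 as applying at 18 women per catchment. At the low end the gain is negligible.

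A reader might go on to infer a biased effect estimate, an inflated false-positive rate or a wrong sample size. None of these is shown. This is a weakness in pre-specification and efficiency that should be corrected because correction is cheap; it is not a fatal flaw.

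**What to change.** Replace the imbalance rule with a fixed adjustment set, named before endline data are seen and kept whatever the observed balance:

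- **Facility type**, so that the analysis follows the stratified randomisation. As it does not change between waves, little precision should be expected from it, and none is counted above.
- **Prognostic covariates from the sponsor's own list that treatment is unlikely to change**, such as age, marital status, education, household wealth and distance to the facility. Religion and ethnicity could be added if judged prognostic. Parity is better left out, because endline parity could itself respond to treatment.
- **Own-wave measurement**: each covariate is taken from the woman's own survey, because endline women have no baseline values.

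Report the unadjusted DiD as a sensitivity analysis, use balance tables for description only, and state that the same set applies to the Aim 2 models on the women's survey.

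The cost is a short rewording of the analysis section and a few degrees of freedom out of 4,536 records. No new kind of data is needed, provided the listed characteristics are asked in both surveys.

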1.1 Statistical Methods

Intervention protocol template_Draft_29AUG2016

Our approach to testing the working hypothesis will be to use a difference-in-difference (DiD) model to estimate differential change over time in each of the two treatment areas versus the control area. The rationale for this aim is that the results will contribute to a nascent body of literature on the impact of social accountability interventions on family planning use. We expect to identify the potential contribution of social accountability efforts to increased contraceptive use. Such findings are important because they inform much needed knowledge of effective strategies for reducing unmet need for women living in LICs.

6.1 Sample Size and Power

For the *individual*-level surveys, we estimate a design effect of 1.56 for modern contraceptive prevalence due to our cluster-based sampling procedure, based on information provided in the 2014 Kenya Demographic and Health Survey (KDHS) Final Report, Appendix B, Table B2. We calculate our necessary sample size assuming 1.) 50% current modern contraceptive prevalence in Kisumu; 2.) 42 clusters in each study arm [clusters=facility catchment areas (All public facilities have a catchment area which is clearly defined, mutually exclusive, and exhaustive); we are allowing for potential closure of one facility per arm)]; 3.) an effect size of two standard deviations (which correlates to a change in the prevalence of modern contraceptive use of approximately 10 percentage points). With these parameters, we will need to survey 18 women in each of the 42 clusters in each of the three study arms, resulting in a total sample size of 2,268 women of reproductive age in the individual-level surveys. The 18 women sampled from each cluster will be selected at random. We will follow KDHS procedures in cases where there is more than one eligible woman in the household.

For the *facility*-level surveys we will measure family planning service quality and negative provider behaviors via interviews with one to ten providers, depending on total staff at each of the 147 facilities. This will result in approximately 385 provider interviews, with approximately 128 in each study arm. Unannounced visitors and mystery clients will also be deployed to secure less biased estimates of provider absenteeism, informal fee solicitation, and disrespectful/biased treatment of clients; mystery clients will also collect data on traditional measures of family planning service quality such as choice of methods and information on side effects. All 147 facilities in Kisumu will receive two unannounced visits and three mystery client visits.

Post-treatment, we will repeat the individual-level survey, within a newly sampled cross-section of the population. We will also repeat all facility-level data collection in all 147 public facilities in the county. The changes in contraceptive use, quality of care, and community engagement resulting from the Community Score Card and the Citizen Report Card interventions will be evaluated via data collected in these pre- and post-intervention surveys. The sampling frame for both individual-level surveys will come from the Kenyan National Bureau of Statistics, which completed a new household-level census in all counties in Kenya in August 2019.

7 STUDY INTERVENTION (drug, device or other intervention details)

- Description

The Community Score Card Approach

In the Community Score Card approach, community members come together to document challenges they encounter when seeking services and develop a corresponding set of indicators that can be used to produce a validated facility score. The score is shared with the community and a collaborative process between key community members and facility staff takes place to develop feasible solutions

and a strategic action plan.

Step 1: Preparation (3 months). During this phase, the PI will consult with the Kisumu County Health Director to confirm the geographic coverage of the community score card intervention (the catchment area of the 43 public healthcare facilities in this arm). Training manuals and facilitation guides will be developed. Experienced facilitators will be identified and trained in the community score-card approach. The communities and facility staff will be engaged and sensitized to the community score card via a meeting that discusses the community score card purpose and approach; a date, location, and general process for conducting the community score cards will be selected/designed.

Step 2: Conducting the community score card with target communities (1 month). During this phase, all communities associated with the targeted facilities will assess the primary barriers to quality family planning service delivery and develop corresponding indicators, assisted by an experienced facilitator. The communities will then each complete the score card and generate ideas for quality improvement.

The first activity in this phase will be to divide the community into groups based on shared characteristics. Groups will be determined using a social mapping exercise with a diverse group of community members who know the community well and are able to identify vulnerable households. The social mapping exercise is designed to ensure marginalized populations are included in the score card activities. Possible groups determined by the social mapping exercise may include women, young women, men, young men, female headed-households, households with orphans, and people living with HIV/AIDS.

Once the groups have been determined, a facilitator with a relationship of trust within each group will be identified and assigned to facilitate each group in a participatory manner. Of note, groups will meet in separate areas when developing their scorecard. Each group will be invited to generate a list of issues related to the delivery of healthcare services, with an emphasis on family planning services. The facilitator will elicit issues by asking questions like, *"How are things going with health services at your public facility? What is going well? What is not going well?"* For all issues generated, the facilitator will ask for suggestions of how to improve service delivery. Additionally, because a large number of issues may be identified, group members will also be asked to prioritize issues by agreeing on the most important and urgent issues to resolve first. This information will be fed into an issue matrix. Each group will decide for themselves the issues, solutions, and priorities in their matrix.

Information from the issue matrix will be used by study team members to develop the scorecard indicators for the larger community. Each of the groups will be given a scoring matrix of final indicators and will score these indicators (a suitable scoring system will be developed with community input). Study team members, collaborating with community members, will meet to consolidate scores across groups.

Step 3: Conducting the community score card with family planning providers (1 month – simultaneous with Step 2). Family planning providers in the target facilities will meet and determine the barriers to high quality family planning service delivery. Providers will decide on priority areas and make suggestions for improving service delivery. This step will be similar to step 2, using the same participatory facilitation methods, but the pace may be quicker as providers generally form only one group and have a higher literacy level. Providers may derive a similar list of issues/indicators as the community. When scoring the indicators, the facilitator will be sure to include the views of quieter providers.

Step 4: Connecting the patients and providers and determining an action plan (1 month). This is where community members and service providers share their respective scorecards and jointly develop an action plan. A skilled facilitator with strong negotiation skills will ensure the meeting is positive and productive. Family planning patients and providers - as well as community leaders and process facilitators - will come together to present their findings and to jointly determine the priority areas and develop an action plan. Within the action plan, agreed upon responsibilities will be assigned and a timeline will be communicated. For example, one priority issue may be punctuality of staff and the determined action may be for staff to observe official hours. This action would be led by the providers, in collaboration with the facility manager, and the expected timeline/date of completion may be the following month.

The Citizen Report Card Approach (CRC)

In this approach, individual-level feedback is collected from actual clients of target facilities, via a structured questionnaire, to assess facility performance and generate a public record of service quality. In addition to sharing the final report card with communities, engaged policymakers are invited to use the citizen feedback to improve service delivery.

Step 1: Preparing for data collection and dissemination (1 month). The PI will consult with the Kisumu County Health Director to confirm the geographic coverage of the citizen report card. The PI will also collaborate with staff in the county health office to develop a post-survey publicity strategy. The strategy could include community dialogues, radio call-in shows, television, and newspaper coverage.

Step 2: Designing the CRC survey (3 months). We will conduct three focus groups (two with family planning clients stratified into younger versus older women and one with service providers). This will help to identify key service challenges and inform the content of the CRC questionnaire by allowing citizens to articulate and prioritize relevant indicators for monitoring and reporting on service provider performance. Focus groups with service providers may elicit suggestions for the type of feedback they would find most useful for improving their service delivery. *In general, both providers and clients will be asked about the problem areas related to family planning service delivery*. Once focus group discussions are completed and the data are analyzed, investigators will identify the prominent themes related to family planning service delivery that emerge from the focus group data. In turn, these themes will inform the main content of the CRC questionnaire.

All survey questions wll be grouped into modules including demographic characteristics (age, marital status, education, etc.), contraceptive use, and service quality indicators. Survey questions will be translated into local languages and retranslated back to English to confirm accuracy of translations. Once drafted and translated, the CRC questionnaire will be field-tested in a neighboring county. Prior to survey implementation, communities in the catchment area of the selected facilities will be sensitized to the survey, in collaboration with the county health director and the primary elder for each community.

Step 3: Execute the survey (3 months). The survey will be administered within a representative sample (N=300, ideal size to capture representative community opinions on facility performance, per recommendation of report card developers) of reproductive age women in the catchment areas of facilities randomized to the Citizen Report Card study arm. To obtain a representative sample of women from each catchment area, we will use a multi-stage sampling design in which government census enumeration areas from the 2019 national census will serve as primary sampling units. Within each selected unit, a random sample of 25 households will be selected, during which a list of usual household residents will be obtained. To obtain the list of household residents, a trained enumerator will approach the household head to explain the

study and obtain permission to list household residents. All eligible women aged 18–49 on the household list will be approached by a trained and experienced female enumerator who will explain the study purpose. Eligible women will be asked to participate in the survey via an informed consent protocol; those providing written consent will be interviewed by a female enumerator who will record responses on a password-protected and encrypted electronic device. The interview will not exceed 30 minutes. Pre-survey filters will exclude those women who do not use family planning obtained from a public facility (this cannot be ascertained during the household listing with the household head (often male) as women may use family planning covertly). Thorough quality checks (spot monitoring of interviews and data checks for inconsistent responses) will be conducted.

Step 4: Analyze the data (2 month). We will analyze data from the CRC questionnaire and translate results into a report card. Prior to dissemination, we will conduct cognitive interviews with a convenience sample of 20 people to inform the design and presentation of 'user-friendly' results; this will help to ensure citizens can easily and quickly absorb the findings. The report card will also be translated into the local languages (Kiswahili and Dholuo) so that it is accessible to a broad range of stakeholders.

Step 5: Disseminate results to the community (1 month). Extensive dissemination activities will ensure the Citizen Report Card is widely shared with members of the community. Report card findings will be presented at a high-profile press conference and press kit materials with short, readable stories will be distributed to members of the print, radio, and television media. The goal is to create a public record of service quality

